4.2.4 Management of toxicity of olaparib

Any toxicity observed during the course of the study could be managed by interruption and/or dose reduction of the dose if deemed appropriate by the Investigator. Repeat dose interruptions are allowed as required for a maximum of 14 days on each occasion. If the interruption is any

longer than this, the sponsor or their designee must be informed. Olaparib must be interrupted until the subject recovers completely or the toxicity reverts to the National Cancer Institute (NCI) Common Terminology Criteria for Adverse Events version 4.03, grade 1 or less.

Where toxicity reoccurs following re-challenge with olaparib, and where further dose interruptions are considered inadequate for management of toxicity, then the subject should be considered for dose reduction or must permanently discontinue treatment with olaparib.

Treatment must be interrupted if any NCI-CTCAE grade 3 or 4 adverse event occurs that the Investigator considers to be related to administration of olaparib.

All dose reductions and interruptions (including any missed doses), and the reasons for the reductions/interruptions are to be recorded in the electronic case record form (eCRF).

Management of anemia

Adverse events of anemia CTCAE grade 1 or 2 (Hemoglobin [Hb] ≥ 8 g/dl) should be investigated and managed as deemed appropriate by the Investigator with or without interruption of study drug or change in dose, taking into account previous history of anemia. Common treatable causes of anemia (eg, iron, vitamin B12 or folate deficiencies, and hypothyroidism) should be excluded. In some cases, management of anemia may require blood transfusions. However, if a subject develops anemia CTCAE grade 3 (Hb < 8 g/dl) or worse, study treatment should be interrupted for up to maximum of 4 weeks to allow for bone marrow recovery, and the subject should be managed appropriately. Study treatment can be restarted at the same dose if Hb has recovered to ≥ 10 g/dl or baseline. Any subsequently required anemia related interruptions, considered likely to be dose related, or coexistent with newly developed neutropenia, and or thrombocytopenia, will require Olaparib study treatment dose reductions to 250 mg bid as a first step and to 200 mg bid as a second step.

If a subject has been treated for anemia with multiple blood transfusions without study treatment interruptions and becomes blood-transfusion dependent—as judged by the Investigator— study treatment should be permanently discontinued.

Management of neutropenia and leukopenia

An adverse event of neutropenia and leukopenia should be managed as deemed appropriate by the Investigator with close follow-up and interruption of study drug if CTC grade 3 or worse neutropenia occurs. Primary prophylaxis with granulocyte colony-stimulating factor (G-CSF) is not recommended; however, if a subject develops febrile neutropenia, Olaparib study treatment should be stopped and appropriate management including G-CSF should be given according to local hospital guidelines. Please note that G-CSF should not be used within at least 24 h of the last dose of Olaparib study treatment.

Olaparib treatment can be restarted at the same dose if an adverse event of neutropenia or leucopenia have been recovered up to CTC AE grade ≥ 1 (absolute neutrophil count

$\geq 1.5 \times 10^9/L$). Growth factor support should be stopped at least 24h before restarting study drug (7 days for pegylated G-CSF).

Any subsequent interruptions will require study treatment dose reductions to 250 mg bid as a first step and to 200 mg bid as a second step for a 300 mg monotherapy starting dose.

Management of thrombocytopenia

An adverse event of thrombocytopenia should be managed as deemed appropriate by the Investigator. If a subject develops thrombocytopenia CTCAE grade 3 or worse, study treatment should be interrupted for a maximum of 4 weeks. In some cases, management of thrombocytopenia may require platelet transfusions. Platelet transfusions should be done according to local hospital guidelines.

Management of prolonged hematological toxicities while on study treatment

If a subject develops prolonged hematological toxicity such as:

- ≥ 2 -week interruption/delay in study treatment due to CTC grade 3 or worse anemia and/or development of blood transfusion dependence
- ≥ 2 -week interruption/delay in study treatment due to CTC grade 3 or worse neutropenia (absolute neutrophil count $< 1 \times 10^9/L$)
- ≥ 2 -week interruption/delay in study treatment due to CTC grade 3 or worse thrombocytopenia (platelets $< 50 \times 10^9/L$)

Weekly differential blood counts including reticulocytes (calculate reticulocyte index (RI), $RI = \text{reticulocyte count} \times \text{hematocrit (Hct)}/\text{normal Hct}$; a value of 45 is usually used for normal Hct), and a peripheral blood smear should be performed. If any blood parameters remain clinically abnormal after 4 weeks of dose interruption, the subject should be referred to hematologist for further investigations. Bone marrow analysis and/or blood cytogenetic analysis should be considered at this stage according to standard hematological practice.

Development of a confirmed MDS or other clonal blood disorder should be reported as an SAE. Study treatment should be discontinued if diagnosis of MDS is confirmed.

The dose of olaparib **must not** be adjusted under any other circumstances unless the site Principal Investigator (PI) has provided a prior agreement.

Management of neutropenia, leukopenia and thrombocytopenia

Toxicity	Study treatment dose adjustment
CTCAE Grade 1-2	Investigator judgment to continue treatment or if dose interruption, this should be for a maximum of 4 weeks; appropriate supportive treatment and causality investigation

Toxicity	Study treatment dose adjustment
CTCAE Grade 3-4	Dose interruption until recovered to CTCAE gr 1 or better for a maximum of 4 weeks. If repeat CTCAE grade 3-4 occurrence, dose reduce olaparib to 250 mg twice daily as a first step and 200 mg twice daily as a second step

Olaparib Dose reductions for study treatment

Initial Dose	Dose reduction 1	Dose reduction 2
300mg twice daily	250mg twice daily	200mg twice daily

Management of new or worsening pulmonary symptoms

If new or worsening pulmonary symptoms (eg, dyspnea) or radiological abnormality occurs, an interruption in olaparib dosing is recommended, and a diagnostic workup (including a high resolution CT scan) should be performed to exclude pneumonitis. Following investigation, if no evidence of abnormality is observed on CT imaging and symptoms resolve, then olaparib treatment can be restarted, if deemed appropriate by the Investigator. If significant pulmonary abnormalities are identified, these need to be discussed with the site PI.

Management of nausea and vomiting

Events of nausea and vomiting are known to be associated with olaparib treatment. In study D0810C00019, nausea was reported in 71% of the olaparib-treated subjects and 36% in the placebo-treated subjects; vomiting was reported in 34% of the olaparib-treated subjects and 14% in the placebo-treated subjects. These events are generally of mild to moderate (CTCAE grade 1 or 2) severity, intermittent, and manageable on continued treatment. The first onset generally occurs in the first month of treatment, with the incidence of nausea and vomiting not showing an increase over the treatment cycles. Both nausea and vomiting were reported to be intermittent for the majority of patients and can be managed by dose interruption, dose reduction and/or antiemetic therapy.

No routine prophylactic anti-emetic treatment is required at the start of study treatment; however, subjects should receive appropriate anti-emetic treatment at the first onset of nausea or vomiting and as required thereafter, in accordance with local treatment practice guidelines.

Renal Impairment

If subsequent to study entry and while still on study therapy, a patient's estimated CrCl falls below the threshold for study inclusion (≥ 51 ml/min), retesting should be performed promptly.

A dose reduction is recommended for patients who develop moderate renal impairment (calculated creatinine clearance by Cockcroft-Gault equation of between 31 and 50 ml/min) for any reason during the course of the study: the dose of olaparib should be reduced to 200mg BD.

Because the CrCl determination is only an estimate of renal function, in instances where the CrCl falls to between 31 and 50 mL/min, the investigator should use his or her discretion in determining whether a dose change or discontinuation of therapy is warranted.

Olaparib has not been studied in patients with severe renal impairment (creatinine clearance \leq 30 ml/min) or end-stage renal disease; if patients develop severe impairment or end stage disease it is recommended that olaparib be discontinued.

Hepatic Impairment

If subsequent to study entry and while on study therapy, the patient develops hepatic impairment, the investigator should make every attempt to identify the underlying reason for the impairment.

Olaparib can be administered to patients with mild or moderate hepatic impairment (Child-Pugh Classification A or B) with no dose adjustment. Olaparib has not been studied in patients with severe hepatic impairment and is NOT recommended for use in these patients.

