1.5 Rationale for drug dosing in this study

1.5.1 Rationale for dose of olaparib

As of 15 December 2018, approximately 10682 patients are estimated to have received olaparib in clinical programmes, investigator sponsored studies and collaborative group studies. An estimated 6956 subjects with ovarian, breast, gastric, pancreatic, and a variety of other solid tumors are estimated to have received treatment with olaparib across the dose range 10 mg once daily to 600 mg twice daily (bid) in AstraZeneca-sponsored, investigator-sponsored, and collaborative group studies. The recommended monotherapy tablet dose of olaparib is 300 mg bid. Olaparib is generally well tolerated at monotherapy doses of 300 mg bid (tablet formulation) in subjects with solid tumors. Toxicities such as hematological, gastrointestinal, eg, nausea, vomiting and diarrhea, anorexia, dysgeusia, fatigues, etc., are generally Grade 1 or Grade 2.

This study will use olaparib at the recommended monotherapy tablet dose of 300 mg bid.

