3.4 Inclusion Criteria

Subjects must meet all of the below criteria to be eligible for randomization and study treatment.

1. Age \geq 21 years of age
2. ECOG performance status 0-2
3. Inoperable locally advanced or metastatic breast cancer not amenable to resection with curative intent and histologically confirmed to be estrogen receptor (ER) negative, progesterone receptor (PR) negative, and HER2 negative:
 - ER negative status is defined as $< 1\%$ tumor cells positive for ER by immunohistochemistry (IHC), irrespective of staining intensity
 - PR negative status is defined as $< 1\%$ tumor cells positive for PR by IHC, irrespective of staining intensity
 - NOTE: Enrollment is permitted for ER/PR low-expression subjects (defined as $\leq 10\%$) who are expected to benefit from this trial at the investigator's discretion.
 - HER2 negative status is determined by:
 - IHC 1+, as defined by incomplete membrane staining that is faint/barely perceptible and within $> 10\%$ of invasive tumor cells, or
 - IHC 0, as defined by no staining observed or membrane staining that is incomplete and is faint/barely perceptible and within $\leq 10\%$ of the invasive tumor cells, or
 - FISH negative based on:
 - Single-probe average HER2 copy number < 4.0 signals / cell, or
 - Dual-probe HER2/CEP17 ratio < 2.0 with an average HER2 copy number < 4.0 signals / cell

4. Minimum six 1-weekly doses or three 3-weekly doses of platinum chemotherapy (monotherapy or combination therapy at investigator's discretion) with stable disease (SD), partial response (PR) or complete response (CR) to the platinum therapy as assessed by investigator.
5. Has received no more than 2 prior chemotherapy lines for metastatic breast cancer including current platinum-based chemotherapy.
6. Able to provide a representative formalin-fixed, paraffin embedded tumor specimen archival or fresh tissue for correlative studies and biomarker analysis.
7. Hemoglobin ≥ 9.0 g/dL and no blood transfusions in the 28 days prior to study entry. Absolute neutrophil count $\geq 1,500/\text{mm}^3$. Platelet count $\geq 100 \times 10^9/\text{L}$.
8. Total bilirubin $< 1.5 \times$ the upper limit of normal (ULN) with the following exception: subjects with known Gilbert's disease who have serum bilirubin $< 3 \times$ ULN may be enrolled.

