9. Aspartate transaminase (AST) and alanine transaminase (ALT) $< 2.5 \times$ ULN with the following exceptions: subjects with documented liver or bone metastases may have AST and ALT $< 5 \times$ ULN.
10. Alkaline phosphatase (ALP) $< 2 \times$ ULN ($< 5 \times$ ULN in subjects with known liver involvement and $< 7 \times$ ULN in subjects with known bone involvement).
11. Serum creatinine $< 1.5 \times$ ULN or creatinine clearance > 51 mL/min by the Cockcroft-Gault formula (Cockcroft and Gault 1976) or by 24-hour urine collection for determination of creatinine clearance.
12. For subjects of childbearing potential, agreement (by both subject and partner) to use two effective forms of contraception, including surgical sterilization, reliable barrier method, birth control pills, contraceptive hormone implants, or true abstinence and to continue its use for the duration of the study and for 3 months after last dose of study treatment.
13. Subjects of childbearing potential should have a negative urine or serum pregnancy test during their screening visit. If the urine test is positive or cannot be confirmed as negative, a serum pregnancy test will be required.

14. Subjects willing and able to comply with the protocol for the duration of the study including undergoing treatment and scheduled visits and examination.
15. For inclusion in genetic research, subjects must provide informed consent for genetic research collection of specimens to be stored at repository for future research.

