4.2.2 Olaparib

Olaparib (AZD 2281) (as film-coated tablet formulation) is intended for oral administration. The tablet monotherapy dose and the dose that will be used in this study is 300 mg bid taken continuously in 28 day cycles.

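### Inclusion criterion 11 does not impose the creatinine clearance floor of 51 mL/min that Section 4.2.4 treats as the entry threshold, and no renal rule covers impairment present at entry

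*Combined protocol and SAP*

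**What the plan says.** Section 3.4 opens with "Subjects must meet all of the below criteria to be eligible for randomization and study treatment". Criterion 11 there is met by serum creatinine below 1.5 x "ULN or creatinine clearance > 51 mL/min by the Cockcroft-Gault formula" (or by 24-hour urine collection). The two limbs are joined by 'or', and nothing else in Sections 3.4 or 3.5 limits clearance.

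Section 4.2.4, under Renal Impairment, asks for prompt retesting if a patient's "estimated CrCl falls below the threshold for study inclusion", and gives that threshold as 51 mL/min or more. It continues: "A dose reduction is recommended for patients who develop moderate renal impairment", defined as clearance of 31 to 50 mL/min, "for any reason during the course of the study: the dose of olaparib should be reduced to 200mg BD". In that range "the investigator should use his or her discretion in determining whether a dose change or discontinuation of therapy is warranted". For clearance of 30 mL/min or less, it says olaparib has not been studied and recommends discontinuation if patients develop it.

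The starting dose is the same for all. Section 1.5.1: "This study will use olaparib at the recommended monotherapy tablet dose of 300 mg bid". Section 4.2.2: "the dose that will be used in this study is 300 mg bid taken continuously in 28 day cycles".

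**The concern.** Section 4.2.4 relies on an entry floor that criterion 11 does not contain. Because the limbs are alternatives, the clearance limb can only widen eligibility, by admitting subjects whose creatinine is at or above 1.5 x ULN. It can never exclude a subject whose creatinine is below that limit.

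The dosing rules do not close the gap. Each is tied to a change after entry: the retest applies to clearance that falls on therapy, and the reduction and discontinuation advice apply to patients who develop impairment. A subject who enters with clearance of 31–50 mL/min, or of 30 or less, has no written starting dose other than 300 mg bid.

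What is at stake is subject safety and consistent handling across sites. The documents give no exposure or toxicity data by renal function, so the size of any harm cannot be stated.

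**Working it through.** There is no sample size, power or alpha figure to reproduce. The question is whether creatinine below 1.5 x ULN implies clearance of at least 51 mL/min.

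**Inputs**
- Clearance cut-offs of 51 and 30 mL/min: Section 4.2.4.
- Creatinine limit of 1.5 x ULN: criterion 11.
- Minimum age 21, no upper limit: criterion 1. No minimum weight is set.
- Weight 75 kg: the average used for durvalumab dosing in Section 1.5.2, not a trial average. Weight 50 kg: assumed.
- Creatinine ULN: not in the documents. Assumed 1.0 mg/dL, range 0.9 to 1.2, so 1.5 x ULN is 1.5 mg/dL (1.35 to 1.8).

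**Formula** (Cockcroft-Gault, women)

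CrCl = (140 − age) x weight x 0.85 / (72 x Scr)

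Solving for the age above which CrCl is below T:

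threshold age = 140 − T x 72 x Scr / (0.85 x weight)

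For example, T = 51, Scr 1.0, 50 kg: 140 − 51 x 72 x 1.0 / (0.85 x 50) = 140 − 86.4 = 53.6, so from age 54 in whole years.

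**Threshold ages** (in brackets: ULN 0.9; ULN 1.2)

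| Cut-off T | Creatinine | Weight | Threshold age | First whole year |
|---|---|---|---|---|
| 51 | at ULN | 75 kg | 82.4 (88.2; 70.9) | 83 (89; 71) |
| 51 | at ULN | 50 kg | 53.6 (62.2; 36.3) | 54 (63; 37) |
| 51 | just under 1.5 x ULN | 75 kg | 53.6 (62.2; 36.3) | 54 (63; 37) |
| 51 | just under 1.5 x ULN | 50 kg | 10.4 (23.4; below 0) | every eligible age (from 24; every eligible age) |
| 30 | just under 1.5 x ULN | 50 kg | 63.8 (71.4; 48.5) | 64 (72; 49) |
| 30 | just under 1.5 x ULN | 75 kg | 89.2 (94.3; 79.01) | 90 (95; 80) |

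**Individual profiles** (ULN 1.0)
- Age 65, 50 kg, Scr 1.0: 75 x 50 x 0.85 / 72 = 44.3 mL/min. Eligible, in the 31–50 band.
- Age 70, 50 kg, Scr 1.49: 70 x 50 x 0.85 / (72 x 1.49) = 27.7 mL/min. Eligible, in the severe range.
- Age 65, 75 kg, Scr 1.0: 75 x 75 x 0.85 / 72 = 66.4 mL/min. Unaffected.
- Age 50, 75 kg, Scr 1.5 (the limit): 90 x 75 x 0.85 / (72 x 1.5) = 53.1 mL/min. Unaffected at ULN 1.0 (59.0 at ULN 0.9), but 44.3 if ULN is 1.2.

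**Dose:** 300 mg bid against the recommended 200 mg BD is 300 / 200 = 1.5 times.

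**The case against.** The strongest reply has four parts.

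- **Discretion.** The 200 mg BD step is a recommendation followed by investigator discretion, because clearance is only an estimate. A subject whose clearance falls to 45 mL/min on study may stay at 300 mg bid, so starting another such subject at that dose does not breach a firm limit. This stands for the 31–50 band and lowers the weight of the 1.5-fold figure. It does not help at 30 mL/min or below.
- **Visibility.** Appendix A schedules a Cockcroft-Gault estimate at screening and every cycle, Section 4.1.4 requires an approved eligibility checklist before randomization, Section 4.2.4 allows other dose adjustments with the site PI's prior agreement, and Section 4.3 requires withdrawal if continuing would be harmful. A low value would therefore probably be noticed. But the checklist would apply criterion 11 as written, and the other provisions permit action without directing a starting dose.
- **Reading.** The 51 mL/min in Section 4.2.4 could be shorthand for the clearance limb of criterion 11, with 'creatinine or clearance' a deliberate choice. That is possible, but the 31–50 band sits directly below 51, which fits an intended floor. On either reading, impairment at entry has no dosing rule.
- **Timing and numbers.** The Extension-period text (for example Section 4.5.2) suggests enrolment may be complete, and the affected group may be small or empty. This stands, and it limits what changing criterion 11 can achieve now.

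**Conclusion.** The concern holds. Followed exactly, the plan can start a subject on 300 mg bid at a clearance for which it recommends 200 mg BD when it arises later, or for which it says the drug has not been studied. The gap exists at every ULN assumed, 0.9 to 1.2 mg/dL. It is confined to older or lighter women, or those with creatinine near the limit; a 75 kg woman with creatinine at ULN is affected only from age 83 (89 to 71).

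The ages rest on the assumed ULN and weights; the textual inconsistency does not. Neither the number of subjects affected nor any harm can be derived from the documents. This is a safety and consistency point worth correcting. It has no bearing on PFS, the 25 subjects per arm (30 with drop-out) or the test.

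**What to change.** 1. **Criterion 11:** require creatinine clearance of at least 51 mL/min, by Cockcroft-Gault or 24-hour urine, for every subject, and remove creatinine below 1.5 x ULN as a sufficient alternative. This also reconciles the strict inequality in criterion 11 (above 51) with the 'at least 51' in Section 4.2.4.
2. **Section 4.2.4:** state that the renal rules apply whether impairment is present at entry or develops later. At 31–50 mL/min, 200 mg BD is recommended with the existing investigator discretion; at 30 mL/min or below, olaparib is not recommended, and discontinuation is advised for anyone already on it.

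The cost is two wording changes and no new test. Some older or lighter subjects would become ineligible in a 60-subject trial; how many cannot be derived. If enrolment is complete, the first change has little forward effect and the second is the one that matters, since it covers subjects already on olaparib.

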4.2.5 Durvalumab

Durvalumab should be given at least 1 hour after the subject has taken their olaparib morning dose. Durvalumab will be administered as an IV infusion over 60 minutes (+/- 5 minutes) at a dose of 1500 mg every 28 days.

Subjects allocated to the combination arm in the study will receive durvalumab via IV infusion at a dose of 1500 mg every 28 days in addition to olaparib tablets 300 mg bid. Treatment with durvalumab will commence on Day 1 of each 28 day cycles and will continue on the recommended schedule until progression of disease, unacceptable toxicity, withdrawal of consent, or other reasons to discontinue treatment occur. Disease progression requires confirmation, treatment with durvalumab will continue between the initial assessment of progression and confirmation of progression. If progression is not confirmed, then the subject should continue on study treatment and on treatment assessments.

4.2.6 Durvalumab: drug preparation

The Investigational Products Supply section of AstraZeneca/MedImmune will supply durvalumab as a 500-mg vial solution for infusion after dilution. The solution contains 50 mg/mL durvalumab, 26 mM histidine/histidine-hydrochloride, 275 mM trehalose dihydrate, and 0.02% (/volume) polysorbate 80; it has a pH of 6.0. The nominal fill volume is

10 mL. Investigational product vials are stored at 2°C to 8°C (36°F to 46°F) and must not be frozen. Durvalumab must be used within the individually assigned expiry date on the label.

For patients weighing >30 kg, a fixed dose of 1500 mg Q4W durvalumab (equivalent to 20 mg/kg Q4W) (based on an average body WT of 75 kg) should be prepared. For subjects ≤30 kg body weight, dose is determined using body weight, calculating the stock volume of durvalumab to achieve the accurate dose according to Appendix D. If a patient weighs exactly 30 kg or less, then patient should receive weight-based dosing for durvalumab.

The dose of durvalumab for administration must be prepared by the Investigator's or site's designated IP manager using aseptic technique. Total time from needle puncture of the durvalumab vial to the start of administration should not exceed:

- 24 hours at 2°C to 8°C (36°F to 46°F)
- 4 hours at room temperature

If in-use storage time exceeds these limits, a new dose must be prepared from new vials. Infusion solutions must be allowed to equilibrate to room temperature prior to commencement of administration.

No incompatibilities between durvalumab and polyvinylchloride or polyolefin IV bags have been observed. Dose of 1500mg durvalumab for patients >30 kg will be administered using an IV bag containing 0.9% (w/v) saline with a final durvalumab concentration ranging from 1 to 20 mg/mL, and delivered through an IV administration set with a 0.2- or 0.22-µm in-line filter.

Remove a volume of IV solution from the IV bag equal to the calculated volume of durvalumab to be added to the IV bag prior to addition of durvalumab. Next, the volume of durvalumab (ie, 30.0 mL for 1500 mg of durvalumab) is added to the IV bag such that final concentration is within 1 to 20 mg/mL (IV bag volumes 100 to 1000 mL). Mix the bag by gently inverting to ensure homogeneity of the dose in the bag.

